6.3 Planned Study Visits

6.3.1 Visit 02, Day 8 (± 1 day), Clinic Visit

The following activities will be performed at Visit 02.

- Obtain interim medical history by interview of subjects and note any changes since the previous clinic visit.
- Record all concomitant medications on the appropriate eCRF.
- Assess all AE/SAEs and record them on the appropriate eCRF.
- Obtain vital signs including oral temperature, blood pressure, and pulse, if indicated based on review of complete medical history.
- A targeted physical examination will be performed, if needed, by a study clinician licensed to make medical diagnoses and listed on Form FDA 1572 as the site PI or sub-investigator, if indicated based on review of complete medical history.
- Assess for reactogenicity phenomena through subject interview and review memory aid.

- Examine vaccination site for local reactions.
- Collect blood samples for immunologic assays as described in the Schedule of Events ([Appendix A](#)).

6.3.2 Visit 03, Day 15 (± 1 day), Clinic Visit

The following activities will be performed at Visit 03.

- Obtain interim medical history by interview of subjects and note any changes since the previous clinic visit.
- Record all concomitant medications on the appropriate eCRF.
- Assess all AE/SAEs and record them on the appropriate eCRF.
- Obtain vital signs including oral temperature, blood pressure, and pulse, if indicated based on review of complete medical history.
- A targeted physical examination will be performed, if needed, by a study clinician licensed to make medical diagnoses and listed on Form FDA 1572 as the site PI or sub-investigator, if indicated based on review of complete medical history.
- Collect blood samples for immunologic assays as described in the Schedule of Events ([Appendix A](#))
- Subjects will be instructed to abstain from receptive anal and/or vaginal intercourse, insertion of anything into their vagina and/or anus, or oral sex for at least 2 days prior to the next study visit

6.3.3 Visit 04, Day 29 (± 1 day), Second Vaccination, Clinic Visit

The following activities will be performed at Visit 04.

- Obtain interim medical history by interview of subjects and note any changes since the previous clinic visit.
- Review interim sexual history to identify any new sexual partners since the last screening visit
- Record all concomitant medications on the appropriate eCRF.

- Review COVID-19 vaccine history to ensure the subject is at least 14 days out from any COVID-19 vaccine before receiving study vaccine.
- Assess all AE/SAEs and record them on the appropriate eCRF.
- Obtain vital signs including oral temperature, blood pressure, and pulse.
- A targeted physical examination will be performed, if needed, by a study clinician licensed to make medical diagnoses and listed on Form FDA 1572 as the site PI or sub-investigator, if indicated based on review of complete medical history.
- Collect venous blood for RPR testing
- Collect pharyngeal and rectal swabs for nucleic acid amplification testing (NAAT) for GC and CT
- Collect urine for NAAT for GC/CT from male subjects
- Collect a self-collected vaginal swab for NAAT for GC/CT from female subjects
- Collect blood samples for immunologic assays as described in the Schedule of Events ([Appendix A](#))
- Collect rectal and oropharyngeal mucosal secretion samples for immunologic assays as described in the Schedule of Events ([Appendix A](#))
- From female subjects, collect vaginal mucosal secretion samples for immunologic assays as described in the Schedule of Events ([Appendix A](#))
- Perform a urine pregnancy test within 24 hours before second vaccination on all female subjects of childbearing potential. Results must be negative and known before second vaccination.
- Perform pre-administration reactogenicity assessments before the second vaccination to establish baseline. Subjects will then receive a single dose of vaccine via IM injection into the deltoid muscle of the preferred arm. The site of injection (right or left arm) and time of administration will be recorded on the appropriate eCRF.
- Observe subjects in the clinic for ≥ 15 minutes after vaccination to monitor for any acute reactions.
- Evaluate the vaccination site and assess for reactogenicity and AE/SAEs for ≥ 15 minutes after vaccination and before discharge from clinic and record on the appropriate CRF.

- Subjects will enter their reactogenicity information in an electronic memory aid (with paper back up). Subjects will be provided a thermometer and ruler (if needed) and will record daily oral temperature, solicited injection site and systemic reactions, any unsolicited AEs, and concomitant medications. Subjects will have their electronic memory aid reviewed with them at their next study visit.

6.3.4 Visit 05, Day 36 (± 1 day), Clinic Visit

The following activities will be performed at Visit 05.

- Obtain interim medical history by interview of subjects and note any changes since the previous clinic visit.
- Record all concomitant medications on the appropriate eCRF.
- Assess all AE/SAEs and record them on the appropriate eCRF.
- Obtain vital signs including oral temperature, blood pressure, and pulse, if indicated based on review of complete medical history.
- A targeted physical examination will be performed, if needed, by a study clinician licensed to make medical diagnoses and listed on Form FDA 1572 as the site PI or sub-investigator, if indicated based on review of complete medical history.
- Assess for reactogenicity phenomena through subject interview and review memory aid
- Examine vaccination site for local reactions
- Collect blood samples for immunologic assays as described in the Schedule of Events (0)
- Subjects will be instructed to abstain from receptive anal and/or vaginal intercourse, insertion of anything into their vagina and/or anus, or oral sex for at least 2 days prior to the next study visit

6.3.5 Visit 06, Day 43 (± 3 days), Rectal Mucosal Biopsy, Clinic Visit

The following activities will be performed at Visit 06.

- Obtain interim medical history by interview of subjects and note any changes since the previous clinic visit.

- Obtain interim sexual history to identify any new sexual partners since the start of the study and the second vaccination visit
- Record all concomitant medications on the appropriate eCRF.
- Assess all AE/SAEs and record them on the appropriate eCRF.
- Obtain vital signs including oral temperature, blood pressure, and pulse.
- A targeted physical examination will be performed, if needed, by a study clinician licensed to make medical diagnoses and listed on Form FDA 1572 as the site PI or sub-investigator, if indicated based on review of complete medical history.
- If indicated based on the subject's interim sexual history: Collect pharyngeal and rectal swabs for NAAT for GC and CT, collect urine for NAAT for GC/CT from male subjects, and collect a self-collected vaginal swab for NAAT for GC/CT from female subjects
- Collect blood samples for immunologic assays as described in the Schedule of Events ([Appendix A](#))
- Collect rectal and oropharyngeal mucosal secretion samples for immunologic assays as described in the Schedule of Events ([Appendix A](#))
- From female subjects, collect vaginal mucosal secretion samples for immunologic assays as described in the Schedule of Events ([Appendix A](#))
- Perform rigid sigmoidoscopy and collect rectal mucosal biopsy samples for immunologic assays as described in the Schedule of Events ([Appendix A](#)) (for subjects in the mucosal biopsy subgroup)
- Subjects will be counseled not to engage in anal intercourse for 1 week after the rectal biopsy procedure.
- Subjects will be instructed to abstain from receptive anal and/or vaginal intercourse, insertion of anything into their vagina and/or anus, or oral sex for at least 2 days prior to the next study visit

6.3.6 Visit 06P, Day 44 (+1 day), Telephone Visit

This visit will take place 24-48 hours after the baseline rectal biopsy procedure only for subjects enrolled in the rectal biopsy cohort. The following activities will be performed at Visit 06P.

- Assess all AE/SAEs from the biopsy procedure and record them on the appropriate eCRF.
- Subjects will be reminded not to engage in anal intercourse for 1 week after the rectal biopsy procedure.
- Subjects will be reminded to abstain from receptive anal and/or vaginal intercourse, insertion of anything into their vagina and/or anus, or oral sex for at least 2 days prior to the next study visit.

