Twenty-four to forty-eight hours after the procedure, study personnel will call the participants who donated rectal biopsy samples and inquire about symptoms, complications, or adverse events related to study procedures. Participants who report symptoms suggestive of any significant complications will receive advice on seeking care and will be given referrals to appropriate healthcare professionals as needed. This follow-up may be completed over the phone or through electronic communication.

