8.6.2 Individual Halting Criteria

A subject will be discontinued from second vaccination if:

- Subject develops a new medical condition or medication change for which continued participation, in the opinion of the investigator, would pose a risk to the subject
- Subject is no longer willing and/or able to adhere to study restrictions outlined in the Inclusion and Exclusion Criteria
- Subject has a fever (defined as an oral temperature $\geq 38.0^{\circ}\text{C}$) or an acute illness at the time of boost vaccination administration. The next study vaccination can be deferred until

the fever or illness resolves or only minor residual symptoms remain, that in the opinion of the investigator, will not interfere with the ability to assess safety parameters as required by the protocol, provided that the boost is given within the protocol-defined study window.

- Subject has received COVID-19 vaccine <14 days prior to scheduled dose #2. The next study vaccination can be deferred until at least 14 days elapse from the time of any COVID-19 vaccination, if in the opinion of the investigator, will not interfere with study assessments as required by the protocol, provided that the boost is given within the protocol-defined study window.
- Permission to administer vaccination outside the protocol-defined study window must be obtained from DMID Medical Officer.

Note: In case the boost vaccination is postponed, the timing of the safety/immunogenicity visits post-boost will be planned relative to actual vaccination day.

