9.5.1 Immunogenicity and Safety Measurements Assessed and Flow Chart

Table 2: Schedule of Study Procedures

Procedures	Screening (Visit 00A) Day -56 to -1 (-56 to -28 for biopsy cohort)	Screening (Visit 00B) Day -7 to -1 (-34 to -28 for biopsy cohort)	Baseline Rectal Mucosal Biopsy Visit 00C ,Day -28 to -1	Study Visit 00P (Phone visit) Day -27 to -12	Enrollment/Baseline visit 1,Day 1	Study Visit 2 Day 8 ±1day	Study Visit 3 Day 15 ±1day	Study Visit 4 Day 29 ±1day	Study Visit 5 Day 36 ±1day	Study Visit 6 Day 43 ±3 days	Study Visit 6p Day 44±1days	Study Visit 7 Day 57 ±1days	Final Study visit Day 18 ±7 days	Early I Termination Visit ¹⁵
Informed consent	X													
Assessment of Eligibility criteria	X	X	X		X									
Demographics	X													
Medical history	X	X	X		X	X	X	X	X	X		X	X	X
Sexual history	X	X	X		X			X		X		X	X	X
Randomization					X									
Concomitant medications	X	X	X		X	X	X	X	X	X		X	X	X
Review covid-19 Vaccine history					X			X						
Vital signs	X	(X)	X		X	(X)	(X)	X	(X)	X		(X)	(X)	(X)
Physical exam	X	(X)	(X)		(X)	(X)	(X)	(X)	(X)	(X)		(X)	(X)	(X)
Administer study intervention					X			X ^e						
Pre-vaccine reactogenicity assessment					X			X						
Post-vaccine, Observation to assess Acute reaction (for ≥ 15 minutes)					X			X						
Evaluation vaccine site, Reactogenicity and AE/SAE after ≥ 15 minutes					X			X						
Memory aid					X ^d	X ^d	X	X	X	X				(X)
AE review and evaluation			X ^d	X ^d	X	X	X	X	X	X	(X)	X	X	X

Table 2: Schedule of Study Procedures (continued)

Procedures		Study Visit Timeline																																							
		Screening (Visit 00A) Day -56 to -1 (-56 to -28 for biopsy cohort)			Screening (Visit 00B) Day -7 to -1 (-34 to -28 for biopsy cohort)			Baseline Rectal Mucosal Biopsy Visit 00C ,Day -28 to -1			Study Visit 00P (Phone visit) Day -27 to -12			Enrollment/Baseline visit 1,Day 1			Study Visit 2 Day 8 ±1day			Study Visit 3 Day 15 ±1day			Study Visit 4 Day 29 ±1day			Study Visit 5 Day 36 ±1day			Study Visit 6 Day 43 ±3 days			Study Visit 6p Day 44±1days			Study Visit 7 Day 57 ±1days			Final Study visit Day 18 ±7 days			Early I Termination Visit ¹⁵
Specimen collection	Hematology (CBC, PT, aPTT) ^a	X	(X)	(X)																																					
	Urine pregnancy test	X	(X)			X											X													(X)											
	STI screening ^b	X ^c				(X)	(X)	(X)	(X)	(X)	(X)	(X)	(X)	(X)	(X)	(X)	(X)	(X)	(X)	(X)	(X)	(X)	(X)	(X)	(X)	(X)	(X)														
	Rectal mucosal biopsy ^a				X															X ^f																					

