10.2 Protocol Deviations

Table 3: Distribution of Protocol Deviations by Category, Type, and Treatment Group

Category	Deviation Type	4CMenB (N=X)		Placebo (N=X)		All Participants (N=X)	
		No. of Part.	No. of Dev.	No. of Part.	No. of Dev.	No. of Part.	No. of Dev.
Eligibility/enrollment	Any type	X	X	X	X	X	X
	Did not meet inclusion criterion	X	X	X	X	X	X
	Met exclusion criterion	X	X	X	X	X	X
	ICF not signed prior to study procedures	X	X	X	X	X	X
	Other	X	X	X	X	X	X
Treatment administration schedule	Any type	X	X	X	X	X	X
	Out of window visit	X	X	X	X	X	X
	Missed visit/visit not conducted	X	X	X	X	X	X
	Missed treatment administration	X	X	X	X	X	X
	Delayed treatment administration	X	X	X	X	X	X
	Other	X	X	X	X	X	X
Follow-up visit schedule	Any type	X	X	X	X	X	X
	Out of window visit	X	X	X	X	X	X
	Missed visit/visit not conducted	X	X	X	X	X	X
	Other	X	X	X	X	X	X
Protocol procedure/assessment	Any type	X	X	X	X	X	X
	Incorrect version of ICF signed	X	X	X	X	X	X
	Blood not collected	X	X	X	X	X	X
	Urine not collected	X	X	X	X	X	X
	Stool not collected	X	X	X	X	X	X
	Other specimen not collected	X	X	X	X	X	X
	Too few aliquots obtained	X	X	X	X	X	X

Table 3: Distribution of Protocol Deviations by Category, Type, and Treatment Group (continued)

Category	Deviation Type	4CMenB (N=X)		Placebo (N=X)		All Participants (N=X)	
		No. of Part.	No. of Dev.	No. of Part.	No. of Dev.	No. of Part.	No. of Dev.
Specimen	Specimen result not obtained	x	x	x	x	x	x
	Required procedure not conducted	x	x	x	x	x	x
	Required procedure done incorrectly	x	x	x	x	x	x
	Study product temperature excursion	x	x	x	x	x	x
	Specimen temperature excursion	x	x	x	x	x	x
	Other	x	x	x	x	x	x
Treatment administration	Any type	x	x	x	x	x	x
	Required procedure done incorrectly	x	x	x	x	x	x
	Study product temperature excursion	x	x	x	x	x	x
	Other	x	x	x	x	x	x
Blinding policy/procedure	Any type	x	x	x	x	x	x
	Treatment unblinded	x	x	x	x	x	x
	Other	x	x	x	x	x	x

Note: N = Number of participants in each group in the safety population

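### The fixed Day 44 (+1) window for the post-biopsy call (Visit 06P) cannot be met within 24-48 hours for biopsies on Days 40, 41, 45 or 46, all of which Visit 06 permits

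*Protocol*

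**What the plan says.** Protocol 6.3.5 sets the second biopsy visit as "Visit 06, Day 43 (± 3 days), Rectal Mucosal Biopsy, Clinic Visit", that is Days 40 to 46.

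Protocol 6.3.6 sets the follow-up call as "Visit 06P, Day 44 (+1 day), Telephone Visit", that is Days 44 to 45, and Appendix A repeats that window. The text of 6.3.6 adds a second rule: "This visit will take place 24-48 hours after the baseline rectal biopsy procedure only for subjects enrolled in the rectal biopsy cohort". The word baseline there matches the sentence used for Visit 00P in 6.1.4.

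Protocol 7.1.1 states the same interval for biopsies generally: "Twenty-four to forty-eight hours after the procedure, study personnel will call the participants who donated rectal biopsy samples".

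The only provision that moves post-boost visits is the note in Protocol 8.6.2: "In case the boost vaccination is postponed, the timing of the safety/immunogenicity visits post-boost will be planned relative to actual vaccination day".

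For the baseline biopsy, the Protocol allows Visit 00C on Day -28 to -14 (6.1.3) and Visit 00P on Day -27 to -12 (6.1.4).

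SAP Table 2 heads the same call "Study Visit 6p Day 44±1days". SAP Table 3 has a line for "Out of window visit" under the follow-up visit schedule.

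**The concern.** Two timing rules apply to one call, and on some permitted biopsy days they cannot both be met. The fixed window fits a biopsy on or next to the nominal Day 43, but Visit 06 has its own allowance of three days either side, and the call window does not move with it.

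The call is where biopsy symptoms are asked about and advice or referral is given. It is the only scheduled contact between Visit 06 and Visit 07 (Day 57 ±1), a gap of 10 days (Day 46 to Day 56) to 18 days (Day 40 to Day 58). AEs related to rectal mucosal sampling are a stated safety parameter (Protocol 8.1 and 8.2), and a procedure-related SAE halts the study (8.6.1). At stake are deviations forced by the schedule and, under one way of resolving the conflict, a later safety call than intended.

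**Working it through.** **Inputs.** Biopsy day b = 40 to 46 (Protocol 6.3.5). Call due 24-48 hours after the procedure (6.3.6, 7.1.1), which in calendar days is b+1 or b+2. Fixed call window: Days 44 and 45 (6.3.6, Appendix A).

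**Reproducing the Protocol's own call window.** For the baseline biopsy, b runs from -28 to -14. The earliest call day is -28 + 1 = -27 and the latest is -14 + 2 = -12. That is exactly the Visit 00P window in 6.1.4, and for every permitted b both call days lie inside it.

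**The same rule applied to Visit 06P.**

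| Biopsy day b | Call days b+1, b+2 | In Days 44-45 |
|---|---|---|
| 40 | 41, 42 | none |
| 41 | 42, 43 | none |
| 42 | 43, 44 | 44 |
| 43 | 44, 45 | 44, 45 |
| 44 | 45, 46 | 45 |
| 45 | 46, 47 | none |
| 46 | 47, 48 | none |

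Four of the seven permitted biopsy days have no compliant call day. Counting in hours, with biopsy and call both between 08:00 and 18:00, gives the same four days.

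**What happens on those days.**

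- Day 40, window kept: the call comes 44 - 40 = 4 to 45 - 40 = 5 days after the biopsy.
- Day 41, window kept: 44 - 41 = 3 to 45 - 41 = 4 days after.
- Day 45: the window closes on the day of the biopsy, before 24 hours have passed.
- Day 46: the window has closed before the biopsy.

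A late call is therefore possible only after a Day 40 or 41 biopsy. After a Day 45 or 46 biopsy, a post-biopsy call meeting the 24-48 hour rule has to be out of window.

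**Does 8.6.2 resolve it?** No. It applies only when dose 2 is postponed, and it then shifts Visit 06 and Visit 06P together. It does not cover a Visit 06 that uses its own ±3 days.

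**A window built as Visit 00P was.** 40 + 1 = 41 to 46 + 2 = 48, so Days 41-48. With the call tied to the actual biopsy, none of the seven days fails.

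**The case against.** The strongest reply is that Day 44 (+1) is simply the 24-48 hour rule written for the nominal biopsy day: 43 + 1 = 44 and 43 + 2 = 45. On that reading the interval after the procedure, stated in both 6.3.6 and 7.1.1, is the operative instruction, and every biopsy day has a valid call time. This is probably how the label arose, and sites would probably follow the interval. But no text says the label moves with the biopsy. The heading has the same study-day form as the other planned visits, whereas Visit 00P was written as a full range. Under Protocol 6.5 any noncompliance with the protocol is a deviation, so a correctly timed call can still be recorded as out of window. SAP Table 3 is a generic shell; it has a line for such records but does not show that this call would be logged there.

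It is also fair that other safety routes exist. At Visit 06 itself, "Subjects will be counseled not to engage in anal intercourse for 1 week after the rectal biopsy procedure", so the reminder in the call repeats advice already given. AEs are assessed again at Visit 07, and participants are told to contact the clinic at once about severe symptoms (Protocol section 11). Protocol 2.3.1 cites a published research series with related AEs in 1.6% of sigmoidoscopy procedures and no SAEs. These points limit the consequence; they do not remove the conflict.

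Three stronger readings are tempting and not supported:

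- That the SAP sets a rival window. Its ±1 stands in a header row that also shows Day 18 for the Day 181 visit and Day -28 to -1 for Visit 00C, where the Protocol has -28 to -14. It may be a transcription slip or a PDF-reading fault, and no planned SAP analysis depends on the timing of this call.
- That the word baseline in 6.3.6 would send a site to the wrong biopsy. A call numbered 06P and dated Day 44 cannot sensibly be timed from a procedure before Day 1.
- That four of seven days means four-sevenths of the participants. The documents do not say how biopsies will spread over Days 40-46; if all fall on Days 42-44, no call is affected.

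**Conclusion.** The point holds as a scheduling inconsistency within the Protocol. For biopsies on Days 40, 41, 45 and 46, no call day satisfies both the fixed Visit 06P window and the 24-48 hour rule. This rests on reading Day 44 (+1) as a study-day window, as it is written, and on counting 24-48 hours as the next day or the day after.

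The size is modest. Only the biopsy cohort (about 20 participants) is concerned. The result is either an unavoidable out-of-window record or, only after a Day 40 or 41 biopsy at a site that keeps to the window, a call 3-5 days after the procedure. How many participants would be affected cannot be derived from the documents. A reader might infer a threat to safety capture overall or to the primary outcome; neither follows, since other AE routes remain and no immunogenicity endpoint uses this visit. It is worth correcting because the schedule cannot be complied with on days it permits and the correction is simple.

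**What to change.** In Protocol 6.3.6 and Appendix A, define Visit 06P as 24-48 hours after the actual Visit 06 biopsy, which gives Days 41-48 overall. Sections 6.3.5 and 7.1.1 need no change.

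As tidying, in 6.3.6 replace the reference to the baseline biopsy with the Visit 06 biopsy, and bring the Visit 6p header in SAP Table 2 into line.

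The cost is a wording change in those places; no contact, procedure or analysis is added.

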6.3.7 Visit 07, Day 57 (± 1 day), Clinic Visit

The following activities will be performed at Visit 07.

- Obtain interim medical history by interview of subjects and note any changes since the previous clinic visit.
- Review interim sexual history to identify any new sexual partners since the last screening visit
- Record all concomitant medications on the appropriate eCRF.
- Assess all AE/SAEs and record them on the appropriate eCRF.
- Obtain vital signs including oral temperature, blood pressure, and pulse, if indicated based on review of complete medical history.
- A targeted physical examination will be performed, if needed, by a study clinician licensed to make medical diagnoses and listed on Form FDA 1572 as the site PI or sub-investigator, if indicated based on review of complete medical history.
- Collect blood samples for immunologic assays as described in the Schedule of Events ([Appendix A](#))
- Collect rectal and oropharyngeal mucosal secretion samples for immunologic assays as described in the Schedule of Events ([Appendix A](#))
- From female subjects, collect vaginal mucosal secretion samples for immunologic assays as described in the Schedule of Events ([Appendix A](#))

- Subjects will be instructed to abstain from receptive anal and/or vaginal intercourse, insertion of anything into their vagina and/or anus, or oral sex for at least 2 days prior to the next study visit

